### 6.5 Pharmacokinetic Analysis Set

The PK Analysis Set comprises all subjects who receive an infusion of CSL346 with at least 1 quantifiable concentration of CSL346 after administration. The actual treatment will be used for subjects in this analysis set.

### 6.6 Pharmacodynamic Analysis Set

The PD Analysis Set comprises subjects in the SAF for whom analysis results were obtained for at least 1 of the exploratory biomarkers of interest. The actual treatment will be used for subjects in this analysis set.

## 7 General Considerations

Datasets submitted to regulatory agencies will be created according to Clinical Data Interchange Standards Consortium (CDISC) standards. Submission data will be provided in Study Data Tabulation Model (SDTM) format. Analysis data will be provided in Analysis Data Model (ADaM) format.

Statistical Analysis System (SAS) version 9.4 or higher will be used to perform all data analyses.

Continuous variables will be summarized in terms of the number of observations (n), mean, SD, median, first quartile, third quartile, minimum and maximum. Other descriptive statistics (e.g. standard error [SE], CV%) may be reported when appropriate. For repeated assessments

of continuous variables, the change from baseline will also be summarized. Categorical variables will be summarized using frequency counts and percentages. Analyses that use other descriptive statistics will have the specific descriptive statistics identified with the analysis in the applicable SAP section.

## **7.1 COVID-19 Impact**

During the course of this study, the global COVID-19 pandemic may still be pervasive, impacting the study in a variety of ways. This section describes how the impact of COVID-19 will be documented.

### **Protocol Deviations**

Protocol deviations due to the COVID-19 pandemic will be collected in the Clinical Trial Management System (CTMS) per the study specific Protocol Deviation Plan or another method as described in the study specific protocol deviations plan.

Covance's CTMS: Pandemic related protocol deviations are identified within CTMS by using the term "COVID-19" as the first term within the deviation description. In addition, the sub-category of 'Other' will be chosen and COVID-19 will be written in the description field.

COVID-19-related protocol deviations will be summarized as sub-categories under existing categories of protocol deviations (see [Section 9.2](#)). All COVID-19 related protocol deviations will appear in the listing of protocol deviations and can be identified based on using the term "COVID-19" as the first term in the description. During the Biostatistics Data Review Meeting a review will be done to ensure that deviations are being marked accordingly.

### **Visit Modality, Missed Visits and Missing Assessments**

Changes to subjects' visits caused by the COVID-19 pandemic will be captured for each subject in electronic data capture (EDC), on the "Visit Status" form. The EDC page is customized with the protocol specific visits and includes different options for the primary visit modality, as well as whether the missed visit/alternate visit modality is due to COVID-19. Changes to visit modality may be a protocol deviation, and this data is captured. Since assessments (e.g. vital signs, laboratory data) collected at each visit are known, the data missing due to COVID-19 can be determined.

Assessments that were missed or required alternate visit modality (e.g. televisits or home health visits) due to COVID-19 will be summarized. In addition the number of subjects with missed visits or alternate visit modality, by visit, will be summarized.

### **Study Treatment Discontinuation or Study Discontinuation**

Subjects who have either study treatment discontinuation or study discontinuation due to

COVID-19 will have the reason captured in the electronic case report form (eCRF). On the appropriate eCRF form to record either study medication discontinuation (“End of Treatment” form) or study discontinuation (“Conclusion of Subject Participation” form), a reason will be selected which includes a field for descriptive text. The reason can be either “Withdrawal by Subject”, “Physician Decision” or “Other”. The associated free text field entry will include “COVID-19”. When either treatment or the study is discontinued due to an AE or death, the specific corresponding AE is collected. Discontinuations due to COVID-19 adverse events (AE) will then be identified based on whether the Medical Dictionary for Regulatory Activities (MedDRA) code for the AE is included in the COVID-19 standard MedDRA query (SMQ) (Narrow).

Cases of study treatment discontinuation or study discontinuation due to COVID-19 will be included in the summary of subject disposition.

### **Adverse Events**

Adverse events associated with COVID-19, which can include a clinically significant laboratory finding like a positive test result for COVID-19, will be reported by investigators following reporting requirements as outlined in the protocol. COVID-19 associated AEs are identified via MedDRA coding. MedDRA version 24.1 has been updated to include COVID-19 specific preferred terms (PT). Relevant AEs will be identified for reporting by use of COVID-19 SMQ (Narrow). A list of those SMQs will be provided by CSL Behring. All COVID-19 associated adverse events will be included in standard AE tables as well as a COVID-19 specific AE table.

A listing showing all COVID-19 associated AEs will be provided.

### **COVID-19 Vaccinations**

For COVID-19 vaccine data collection, sites will be instructed to inquire if subject has received a COVID-19 vaccination and, if answered in the affirmative, should record each dose, exact date of administration, and manufacturer of the vaccine on the concomitant medications form. Standardized Drug Grouping (SDG) from WHO Drug Dictionary will be utilized to identify COVID-19 vaccines (see [Appendix 16.6](#)). Any vaccination related adverse events experienced by study subjects will be recorded on the AE/SAE eCRF page.

The data are planned to be summarized as follows:

- Summary table by SoC and PT of all AEs occurring within 7 days after COVID-19 vaccine administration;
- Listing of all AEs occurring within 7 days after COVID-19 vaccine administration;

- Listing of all subjects receiving COVID-19 vaccine.

### **Overall Summary of Subjects Impacted by COVID-19**

Counts and percentages of subjects with at least one of the following due to COVID-19 will be summarized in an overview table:

- Subjects with any COVID-19 impact;
- Protocol Deviations;
- Missing assessment;
- Missing Visit;
- Alternate Visit Modality;
- Study Treatment Discontinuation;
- Study Discontinuation;
- Any TEAEs;
- Any Serious TEAEs;
- Receipt of COVID vaccine.

## **8 Data Handling Conventions**

### **8.1 Missing Data**

Missing data occurs when any requested data are not provided, leading to blank fields on the collection instrument. These data will be indicated by the use of a “blank” in subject listing displays. Answers such as “Not applicable” and “Not evaluable” are not considered to be missing data and should be displayed as such.

Because of the design and duration of the study, missing data are inevitable. The details of handling missing data are presented in the corresponding sections of this SAP for respective analyses (e.g. primary and secondary efficacy analyses, safety analyses).

### **8.2 General Derived Variables**

#### **8.2.1 Reference Dates and Study Days**

Reference dates are used to assign study periods relative to treatment ([Section 8.4](#)).

- The safety reference date is the treatment start date (date of IV loading dose), and will be used to calculate study day for safety measures.
- The efficacy reference date is the randomization date and will be used to calculate study day for efficacy measures.

- The PK reference date is the date and time of the IV loading dose and will be used to calculate study day/time for PK measures.

The respective study day will be calculated as (date of interest - reference date) + 1 if the date of interest occurs on or after the reference date. If the date of interest occurs before the reference date, then the study day will be calculated as (date of interest – reference date).

There will be no study day zero.

### **8.2.2 Durations**

Durations (e.g. the duration of an adverse event [AE]) are calculated in days as:

- event end date – event start date + 1, if end time or start time not available;
- event end date and time – event start date and time, if both end time and start time available.

Thus, there will be no duration of 0 if end time or start time are not available. If an AE has missing or partially missing start or end date, no duration will be calculated.

To transform durations into weeks, divide the number of days by 7; to report in months, divide the number of days by 30.4375; to report in years, divide the number of days by 365.25. These algorithms return decimal numbers, and ignore the actual numbers of days in the months or years (the calendar days) between start date and stop date. The "year" used in these algorithms is 365.25 days long, and the "month" is one twelfth of that year.

### **8.2.3 Baseline Definition**

Baseline is defined as the most recent, non-missing value before the first IP administration (including unscheduled visits) for all assessments unless otherwise stated. In case of an assessment at the same date as the first IP administration (and only the date for that assessment is available) it will be assumed the assessment was done before IP administration.

For the purposes of the analysis of albumin creatinine ratio, baseline will be defined as the geometric mean of the 6 values obtained before treatment (3 values from Visit 3 and 3 values immediately before treatment at Visit 4). If fewer than 6 values are available, the geometric mean of all the available values will be used for baseline.

Baseline for blood pressure will be the mean of the three values (or all available if fewer than three) collected immediately before the IV loading dose.

Baseline for serum creatinine will be an average of the two samples collected prior to first IP administration (Visit 3 and Visit 4). Baseline eGFR will be calculated based on the baseline

serum creatinine. These calculated baseline eGFR values will be used to define eGFR categories and covariates in statistical analyses.

For soluble tumor necrosis factor receptor 1 (sTNFR1), exploratory circulating and urinary markers, the baseline value will be an average of the two samples collected prior to first IP administration (Visit 3 and Visit 4). [Note: Exploratory circulating biomarkers are defined in [Section 4.1.4](#) as biomarkers of lipid metabolism including but not limited to circulating total cholesterol, triglycerides, high density lipoproteins (HDL), low density lipoproteins (LDL), glycerol, non-esterified fatty acids (NEFA), and ketones. Urinary markers are defined in [Section 10.3](#) as VEGF-A, soluble VEGF receptor 1 (VEGF-R1), kidney injury molecule-1 (KIM-1), neutrophil gelatinase-associated lipocalin (NGAL), clusterin, monocyte chemoattractant protein-1 (MCP-1) and epidermal growth factor (EGF).]

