10.3.3 Safety Analyses

Secondary Endpoints

Treatment-emergent AEs, defined as AEs occurring at or after the start of study treatment, will be summarized for each CSL346 dose level (8 mg/kg and 16 mg/kg) and placebo. An overview summary of AEs, including the number of subjects with any AE; AEs related to study treatment; AEs leading to discontinuation of study treatment; SAEs; and deaths will be produced. Treatment-emergent AEs will be summarized by preferred term and system organ class as well as severity. These analyses will be performed on the Safety Analysis Set. Adverse events of special interest (AESIs) will also be summarized separately.

The analysis of SCr, eGFR, and BP will employ a model similar to the primary endpoint. The analysis for these continuous endpoints is an MMRM analysis of change from Baseline to each postbaseline measurement. Similar to the definition in [Section 10.3.2](#), baseline for these parameters will be the average of the values obtained at Visit 3 and Visit 4 before treatment. The model will include treatment, stratification related to the concomitant use of SGLT2 inhibitors, visit (as a categorical factor), interactions between visit and each of the other model terms, as well as the corresponding baseline measurement as a covariate. As with the primary endpoint analysis, the primary comparison will be of CSL346 (8 mg/kg and 16 mg/kg combined) versus placebo. Exploratory comparisons of CSL346 dose levels with placebo will also be done. These analyses will be performed on the Safety Analysis Set.

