**Table 1 Study Objectives, Endpoints and Summary Measures**

Objectives	Endpoints	Summary Measure(s)
Primary	Change in log-transformed urinary albumin-to-creatinine ratio (ACR) from Baseline to Week 16 (Visit 10)	Geometric mean ratio for CSL346 (8 mg/kg and 16 mg/kg combined) versus placebo (80% confidence interval CI), expressed as percent change from Baseline
Key Secondary	Treatment-emergent adverse events (TEAEs), including adverse events of special interest (AESIs) from the time of first dose of IP through End of Study (EOS)	Number and percentage of subjects overall, by severity, by relatedness, by seriousness, and by action (i.e. IP discontinuation)
	Observed value and change from Baseline in SCr and eGFR through EOS	Mean (standard deviation (SD))
Other Secondary	Observed value and change from Baseline in systolic and diastolic blood pressure (SBP and DBP) through EOS	Mean (SD)
	CSL346 serum PK: Maximum concentration ( $C_{max}$ ) after IV loading dose Time to reach $C_{max}$ in serum ( $T_{max}$ ) after IV loading dose $C_{max}$ after first SC dose $T_{max}$ in serum after first SC dose Area under the concentration-time curve in first dosing interval ( $AUC_{0-\tau}$ ) $C_{trough}$ after each dose	Mean (SD), coefficient of variation (% CV) and geometric mean for all parameters except $T_{max}$ ; Median (minimum, maximum) for $T_{max}$
	Presence of Anti-Drug Antibody (ADA) at Week 4 (Visit 7), Week 8 (Visit 8), and Week 16 (Visit 10)	Number and percentage of subjects with positive result (with reciprocal titer)

Objectives	Endpoints	Summary Measure(s)
Exploratory	Changes from Baseline to each assessment in fasting values for PD biomarkers	Mean (SD)
	Concentration of CSL346 found in urine at Week 1 (Visit 5) and Week 12 (Visit 9)	Mean (SD)
	Number (percent) of patients who regress from macroalbuminuria to microalbuminuria or normoalbuminuria, or from microalbuminuria to normoalbuminuria at Week 16 (Visit 10) compared to Baseline	Number and percentage of subjects

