## **5 Changes from the Protocol Planned Analyses**

The following represent changes in this SAP from the protocol:

- Definition for the Per Protocol Analysis Set has been edited in this SAP and is different from the definition provided in the protocol.
- VEGF-B analyses have been removed as the assay is not available.

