## **10 Efficacy Analyses**

Data for the primary endpoint, ACR, as well as serum creatinine, eGFR, blood pressure and some biomarkers will be collected multiple times after the initiation of treatment, therefore, the primary analysis for these outcomes will be a mixed effects model repeated measures (MMRM) approach. The change from baseline to Weeks 2, 4, 8, 12, 16, and 24 will be included in the model.

Biomarkers of lipid metabolism, glycemic control and novel biomarkers of kidney function will also employ a model similar to the primary endpoint (with the exception of biomarkers measured only at the beginning and end of the study). Exploratory biomarkers will be the subject of a separate report.

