### **10.2 Analysis of Key Secondary Endpoint(s)**

Blood pressure, serum creatinine and eGFR calculated using the Chronic Kidney Disease Epidemiology Collaboration (CKD-EPI) formula [[Levey et al. 2009](#)], [Section 8.2.7](#), will employ a model similar to the primary endpoint. These endpoints will not be log-transformed prior to analysis. The analysis for these continuous endpoints is an MMRM analysis of change from baseline to each post-baseline measurement. The model will include treatment, stratification related to the concomitant use of SGLT2is, visit (as a categorical factor), and interactions between visit and each of the other model terms, as well as the corresponding baseline measurement as a covariate (refer to [Section 16.1](#) for respective SAS code). Hypotheses testing will be identical to that of the primary endpoint. Line graphs of the mean response over time will be provided as well as by ACR status.

All of these analyses will be performed on the ITT Analysis Set.

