#### **10.2.1 Key Secondary Estimand**

The treatment condition and population of the estimand for key secondary endpoints is the same as for the primary endpoint. The variable in each case will be the mean change from baseline through Week 16 in each parameter. Also, in each case, the population level summary will be the arithmetic mean change.

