### **10.3 Analysis of Other Secondary Endpoints**

Biomarkers of lipid metabolism, glycemic control and novel biomarkers of kidney function as well as weight will also employ a model similar to the primary endpoint except for the

concentration of CSL346 in urine. The analysis for continuous endpoints is an MMRM analysis of change from baseline to each post-baseline measurement (Weeks 4, 8 and 16). The model will include treatment, stratification related to the concomitant use of SGLT2i, visit (as a categorical factor), and interactions between visit and each of the other model terms, as well as the corresponding baseline measurement as a covariate (refer to [Section 16.1](#) for respective SAS code). Treatment comparisons of interest will be similar to that of the primary endpoint. Lipid parameters will be natural log transformed prior to analysis.

Urinary biomarkers will be normalized for urine creatinine. These urinary biomarkers include urinary VEGF-A, soluble VEGF receptor 1 (VEGF-R1), kidney injury molecule-1 (KIM-1), neutrophil gelatinase-associated lipocalin (NGAL), clusterin, and monocyte chemoattractant protein-1 (MCP-1) and epidermal growth factor (EGF). Normalization is performed by dividing the urinary biomarker by urine creatinine collected at the midstream morning void taken the same day as the urinary biomarker. Normalized urinary biomarkers should be reported in units of pg/ $\mu$ g. To obtain these units, first convert urinary creatinine from units of mg/dL to units of  $\mu$ g/mL by multiplying by 10. Then divide the urinary biomarker (pg/mL) by urinary creatinine ( $\mu$ g/mL) to get normalized results with units of pg/ $\mu$ g.

A repeated measures analysis of covariance model will be employed to analyze the concentration of CSL346 in urine, collected at Day 1, Day 8, and Day 85. The repeated measures analysis of covariance model will include terms for treatment, baseline as a covariate and SGLT2i use.

All analyses for biomarker will be performed on the PD Analysis Set. Analyses for KIM-1, NGAL, EGF and MCP-1 will be performed in addition for the PP Analysis Set. Analyses for urine CSL346 concentration will be performed on the ITT Analysis Set.

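### The SAP takes the blood pressure baseline from Visit 4 only, an undeclared departure from the protocol's Visit 3/4 average, and disagrees with itself on whether Week 1 enters the BP, SCr and eGFR models

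*SAP*

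**What the plan says.** **Baseline.** Protocol 10.3.3 introduces the models for SCr, eGFR and BP and then states that "baseline for these parameters will be the average of the values obtained at Visit 3 and Visit 4 before treatment". SAP 8.2.3 keeps the two-visit average for SCr and derives baseline eGFR from it. For BP it differs: "Baseline for blood pressure will be the mean of the three values (or all available if fewer than three) collected immediately before"; the reference point is the Day 1 IV loading dose. SAP Section 5 opens with "The following represent changes in this SAP from the protocol" and lists two items, the Per Protocol set definition and the removal of VEGF-B. The BP baseline is not among them, and the SAP modification history does not mention a single-visit BP baseline.

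**Visits in the model.** SAP Section 10 names ACR, SCr, eGFR, BP and some biomarkers together and says "The change from baseline to Weeks 2, 4, 8, 12, 16, and 24 will be included in the model". SAP 10.2, which covers BP, SCr and eGFR, specifies an "MMRM analysis of change from baseline to each post-baseline measurement", and protocol 10.3.3 says the same. The schedule of assessments places BP and biochemistry at Week 1 (Visit 5). First-morning-void urine for ACR is not collected at that visit.

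**The concern.** A change from the protocol's baseline should be visible to a reader of the SAP, and Section 5 is the place for it. The choice of Visit 4 may be deliberate, and it is in line with the SAP's general rule of taking the latest pre-dose value, but no reason is given. In practice, a BP triplicate collected at Visit 3 goes unused in a covariate-adjusted model, which costs some precision.

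On visits, two analysts could fit different models, each with support in the text. The six-week list is the ACR collection schedule. Applied to BP, SCr and eGFR, it leaves out a scheduled visit that protocol 8.1.1 describes as near Tmax and that protocol 1.4 counts among the enhanced safety visits in the first four weeks. The adjusted treatment contrast for these three endpoints at that visit, with its 80% interval, would then not be produced.

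**Working it through.** **1. The plan's own figure.** The documents size only the ACR endpoint. With SD 0.65 and 47 per arm, SE = 0.65 × √(2/47) = 0.134. The one-sided 10% critical value on 92 df then gives a threshold of −0.173, as stated, and power for −0.315 is about 85.5%. This reproduces the plan, and neither part of the present point touches it. No SD, correlation or power is given for BP, SCr or eGFR.

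**2. Cost of the one-visit BP baseline.** The inputs are assumptions: equal variance at each visit, and Visits 3 and 4 equally correlated with Week 16. Let
- T = between-subject variance + visit-to-visit variance;
- r = between-subject variance / T, the correlation of a baseline visit with Week 16;
- c = correlation of Visits 3 and 4.

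Residual variance after adjustment for baseline:
- Visit 4 only: T(1 − r²)
- Visit 3/4 average: T(1 − 2r²/(1 + c))

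For SDs of 12 and 8 mmHg, T = 144 + 64 = 208 and r = 144/208 = 0.692. Visit 4 only gives 208 × (1 − 0.479) = 108.3.

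The trial admits only subjects with SBP ≤ 150 mmHg at Visits 3 and 4 (protocol 4.1.3), which narrows the baseline range. The last column repeats the calculation by simulating 4 million subjects (assumed mean SBP 135) and applying that gate. Simulation error is about 0.1 percentage point.

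| SDs (mmHg) | c | One visit | Two visits | Reduction, no gate | Reduction, with gate |
|---|---|---|---|---|---|
| 12 / 8 | 0.69 | 108.3 | 90.2 | 16.7% | 13.9% |
| 12 / 8 | 0.85 | 108.3 | 100.2 | 7.5% | 6.6% |
| 12 / 8 | 0.90 | 108.3 | 103.1 | 4.8% | 4.4% |
| 10 / 12 | 0.41 | 203.0 | 185.9 | 8.5% | 5.9% |
| 10 / 12 | 0.85 | 203.0 | 199.7 | 1.6% | 1.4% |
| 10 / 12 | 0.90 | 203.0 | 200.9 | 1.1% | 1.0% |
| 15 / 6 | 0.86 | 67.0 | 52.7 | 21.4% | 19.2% |
| 15 / 6 | 0.90 | 67.0 | 56.8 | 15.2% | 13.9% |

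The gated column is the relevant one: 1% to 19% overall, 4% to 14% at 12/8. In standard errors, 1 − √(1 − 0.010) = 0.5% and 1 − √(1 − 0.192) = 10%.

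**3. Visits.** Scheduled post-baseline visits for BP and SCr are Weeks 1, 2, 4, 8, 12, 16 and 24, which is seven. SAP Section 10 lists six. An unstructured covariance has k(k + 1)/2 parameters: 6 × 7/2 = 21 against 7 × 8/2 = 28.

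**4. What the Week 1 contrast adds.** At 12/8, with 47 per arm and a Visit 4 to Week 1 correlation of 0.85:
- baseline-adjusted contrast: √(208 × (1 − 0.85²) × 2/47) = 1.57 mmHg
- difference in raw change: √(2 × 208 × (1 − 0.85) × 2/47) = 1.63 mmHg

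At a correlation of 0.90 the figures are 1.30 and 1.33. What is lost is mainly the planned contrast itself; the precision difference is small.

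**The case against.** The strongest reply is that little depends on either difference. Hypothesis testing for these endpoints follows the primary, whose comparison is at Week 16. No passage names Week 1 as a comparison of interest. The declared summary measure for BP, SCr and eGFR is mean (SD), which the by-visit tables deliver at Week 1 under either reading. This stands, and it is why the point is minor. It does not remove the undeclared departure or tell an analyst which visit list governs.

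Several stronger readings are tempting, and the documents do not support them:

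- **Bias.** A reader might infer that the Visit 4 baseline distorts the treatment comparison. It is a pre-dose value taken the same way in every arm, so it does not.
- **A lost safety signal.** A reader might infer that a rise in BP or SCr at Week 1 would go unseen. The by-visit summaries, the AESI rules, SAP Tables 3 and 4 and IDMC review all remain.
- **AESI counts turning on the baseline.** AESI tables use events marked by the investigator. For the SBP criterion in Table 4, the simulated disagreement between the two baselines is under 0.4% of subject-visits, fewer than 3 of 700 (100 subjects × 7 visits).
- **Conflicting time points.** SAP 10.2.1 says "The variable in each case will be the mean change from baseline through Week 16 in each parameter", while SAP Table 1 has "Observed value and change from Baseline in systolic and diastolic blood pressure (SBP and DBP) through EOS". The first is an estimand variable and the second a descriptive endpoint, and the primary analysis likewise targets Week 16 within data through Week 24.
- **Day 1 post-dose readings in the model.** Visit is a categorical factor and data are reported by nominal visit. These readings belong to Visit 4, so counting them as a modelled visit is strained.
- **The 16.1 code as proof of six visits.** It is written for log ACR. SAP 10.3 cites the same code for biomarkers modelled at "each post-baseline measurement (Weeks 4, 8 and 16"), so it is a template to adapt. For the same reason, the Section 10 list cannot be literal for every endpoint it names.

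**Conclusion.** Both differences are in the text and hold. The BP baseline in SAP 8.2.3 departs from protocol 10.3.3 without being declared. SAP Sections 10 and 10.2 disagree on whether Week 1 enters the BP, SCr and eGFR models. SAP 10.2 is the likelier intent, since it matches the protocol, but the SAP does not say which governs.

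The size is small. For BP the one-visit baseline gives up about 1% to 19% of residual variance, or 0.5% to 10% of the standard error. The low end applies when visit-to-visit noise dominates, or when Visits 3 and 4 are much more alike than either is to Week 16. The range rests wholly on assumed SDs, correlations and mean SBP; only the textual differences are certain. SCr and eGFR baselines already agree with the protocol. The ACR analysis, its power and the Week 16 comparisons remain valid. This is a minor point on secondary endpoints, worth correcting because the data are already collected.

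**What to change.** - **SAP 8.2.3:** define the BP baseline as the average of the Visit 3 and Visit 4 pre-dose triplicate means, using the available visit if there is only one. If Visit 4 alone is intended, declare that in Section 5 with a reason.
- **SAP Section 10:** limit the six-visit list to ACR, and state that the BP, SCr and eGFR models use Weeks 1, 2, 4, 8, 12, 16 and 24.
- **SAP 16.1:** adapt the contrast coefficients to seven visits for these endpoints. That makes 3 × 7 = 21 treatment-by-visit values in place of 18, with Week 16 in sixth position within each arm. State that the covariance fallbacks in 10.1.2 apply.

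The cost is SAP text and code, with no new data. The unstructured covariance grows from 21 to 28 parameters, so a convergence fallback becomes somewhat more likely.
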